Cover letter

Title: Value of contralateral testicular hypertrophy in predicting the status of the intra-abdominal testis?

Running title: contralateral testicular hypertrophy in intra-abdominal testis

Category of the manuscript: Research article

Serial N: 0305079

Document Date: March 19, 2021

I have the honor to submit this original research article entitled "**Does the contralateral testicular volume decide the need for diagnostic laparoscopy in cases of unilateral impalpable undescended testis?**" for clinical registration aiming at your helpful review and hopefully your acceptance for registration.

This manuscript has not been published and is not under consideration for publication elsewhere. The investigators have no conflicts of interest to disclose and this manuscript has not received any financial funds. All of the co-authors, as well as the Alexandria University Scientific Committee, approved its publication and informed consent was signed by the parents explaining the study.

Thank you for your consideration! Waiting for your respectable reply.

Abstract

Background: This study aimed at the evaluation of the value of the estimated volume of a normal testis to predict the status of its contralateral impalpable side and hence decide the importance of laparoscopic exploration.

Methods: Participants with unilateral impalpable maldescended testis – as confirmed by clinical and sonographic examination- were enrolled in this prospective interventional study between November 2018 and August 2022 at Elshatby University Hospital, Faculty of Medicine, Alexandria University. The volume and three-dimensional diameter of the normal contralateral testis were measured by the pre-operative US using the formula: Volume = $L \times W \times H \times \pi/6$, where L is the length, W is the width, H is the height, and was correlated with the intra-operative laparoscopic findings.

Keywords: Impalpable testis; volume; ultrasound

Background

Maldescended testis or cryptorchidism is considered the most common congenital genito-urinary abnormality faced in male neonates with an incidence of 3% in full-term babies and increasing up to 30% in preterm males. However, this incidence declines to about 1% by the age of 3 months as it descends to its normal position in about 80% of cases.^{1,2}

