Only 20 % of maldescended testis is impalpable being either vanishing due to an intra-uterine accident, agenetic, intra-abdominal, or inguinal with different degrees of dysplasia and atrophy.³

The gold standard method for a definitive diagnosis and management of impalpable maldescended testis is laparoscopy and according to its findings; the procedure is planned whether nothing in case of vanishing or agenetic testis, inguinal exploration in case of passing through the DIR or traction, Fowler-Stevens (FS) or one stage laparoscopic assisted orchiopexy in case of the intra-abdominal testis.^{3,4}

The size of the contralateral testis has been used to predict the condition of its contralateral impalpable one while being explored by laparoscopy by many researchers.⁵ Ultrasound (US) is considered by many surgeons as being an accurate, reproducible, and objective in situ tool for the assessment of testicular dimensions and volume.⁶

This study aimed at the assessment of the ability of the three dimensional size as well as the volume of a normal testis as measured by ultrasonography in predicting the status of its contralateral impalpable counterpart and hence deciding the need for proceeding to laparoscopic exploration of this impalpable maldescended testis.

Methods

This prospective interventional study included children with unilateral impalpable maldescended testis presented to Elshatby University Hospital, Faculty of Medicine, Alexandria University from November 2018 to August 2022. Participants with bilateral impalpable maldescended testis and those with post-operative ascended testis were excluded from the study.

After approval of the ethics committee of Alexandria Faculty of Medicine, informed consent was obtained from all parents and legal guardians of the children included in the study. Careful collection of the demographic data of all of the studied participants was followed by careful clinical examination. US abdomen, pelvis, and the inguino-scrotal region performed by the same sonographer were done for:

1. Assessment of the three-dimension diameters as well as the volume of the normal-sided testis. It is measured by the formula: Volume= $L \times W \times H \times \pi/6$, where L is the length, W is the width, and H is the height.
2. Searching for the impalpable testis at all its suspected sites; intra-abdominal, pelvic, or in inguinoscrotal region

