All of the participants were subjected to laparoscopic exploration under general anesthesia with endotracheal intubation and the following data regarding the findings of the affected impalpable side was collected:

- A.** Testicular size in millimeters
- B.** Absent testis: Blind ending vas and vessels
- C.** Present intra-abdominal testis
- D.** Testis passing through the deep inguinal ring (DIR)
- E.** Patency of the DIR on the affected side (closed or open)

The procedure which was done according to the laparoscopic findings was also documented

- A.** Absent testis: Nothing
- B.** Present intra-abdominal testis: Traction 1, Fowler Stephens or laparoscopic assisted orchiopexy
- C.** Testis passing through the deep inguinal ring (DIR): Inguinal exploration and orchiopexy or excision in case of atrophied testis

Statistical Analysis

Data were fed to the computer and analyzed using IBM SPSS software package version 20.0. (Armonk, NY: IBM Corp). The **Shapiro-Wilk** was used to verify the normality of the distribution of variables, Comparisons

between groups for non-parametric variables were assessed using the **Mann Whitney test** or **Kruskal Wallis test**. The significance of the obtained results was judged at the 5% level.

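### The aim is to predict testicular status and decide on laparoscopy, but the plan commits only to rank-based group comparisons and to no measure of diagnostic accuracy

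*Combined protocol and SAP*

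**What the plan says.** The title question in the Cover letter is "Does the contralateral testicular volume decide the need for diagnostic laparoscopy in cases of unilateral impalpable undescended testis". The aim at the end of Background is to assess whether "the three dimensional size as well as the volume of a normal testis", measured by ultrasound, can serve for "predicting the status of its contralateral impalpable counterpart and hence deciding the need for proceeding to laparoscopic exploration".

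The reference standard is available. Background states: "The gold standard method for a definitive diagnosis and management of impalpable maldescended testis is laparoscopy". Methods adds: "All of the participants were subjected to laparoscopic exploration". Methods also defines one outcome category, "Absent testis: Blind ending vas and vessels", and lists two other locations: intra-abdominal, and passing through the deep inguinal ring (DIR). For the DIR group, the documented procedures include excision of an atrophied testis.

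The Statistical Analysis section names SPSS, Shapiro-Wilk for normality, comparisons "between groups for non-parametric variables were assessed using the" Mann-Whitney or Kruskal-Wallis test, and a 5% significance level. The Abstract says the ultrasound measurement "was correlated with the intra-operative laparoscopic findings", without naming a statistic.

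**The concern.** This is a diagnostic-accuracy question with an index test (ultrasound volume and diameters) and a reference standard applied to everyone. The error that matters for the laparoscopy decision is to call a testis absent when it is present. A rank-test p-value does not estimate how often that happens, and nothing else in the plan does. The study could meet its only stated criterion, significance at 5%, and leave its title question unanswered.

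The Statistical Analysis section also does not name the compared variable or say how the three laparoscopic findings are grouped. If all three are compared at once, a significant result can come from a difference between the two kinds of present testis, with no separation of absent from present.

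**Working it through.** The plan has no figure to reproduce: it states no sample size, proportion absent, spread, cut-off or accuracy target. Everything below is therefore assumed and varied, and shows what can happen, not what is likely. The 5% level is taken as two-sided.

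**1. What a just-significant Mann-Whitney result implies.** Let n1 boys have an absent testis and n0 a present one, with n = n1 + n0. A positive test is a call of absent. Assume an equal-variance binormal model without ties.

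- Null SE of the AUC = sqrt((n + 1)/(12 × n1 × n0)); just-significant AUC = 0.5 + 1.96 × SE
- Separation d = sqrt(2) × z(AUC)
- Youden point: sensitivity = specificity = Φ(d/2)
- At 95% specificity: sensitivity = Φ(d − 1.645)
- Share of absent calls that are wrong = 1 − PPV

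Example with n = 100 and 40% absent:

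- SE = sqrt(101/(12 × 40 × 60)) = 0.0592, AUC = 0.616, d = 0.417.
- Youden point: Φ(0.209) = 0.583; wrong share = 0.6 × 0.417/(0.6 × 0.417 + 0.4 × 0.583) = 0.518.
- At 95% specificity: Φ(0.417 − 1.645) = 0.110; wrong share = 0.6 × 0.05/(0.6 × 0.05 + 0.4 × 0.110) = 0.406.
- Expected number called absent at 95% specificity: 100 × (0.4 × 0.110 + 0.6 × 0.05) = 7.4.

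Four values in a cell are for 20/40/60/70% absent:

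| n | AUC | Wrong share, Youden | Sensitivity at 95% specificity | Wrong share at 95% specificity | Called absent at 95% specificity |
|---|---|---|---|---|---|
| 60 | 0.68/0.65/0.65/0.66 | 70/49/30/21% | 17/14/14/14% | 55/36/20/13% | 4.4 to 7.0 |
| 100 | 0.64/0.62/0.62/0.62 | 73/52/32/23% | 13/11/11/12% | 61/41/23/16% | 6.6 to 9.6 |
| 200 | 0.60/0.58/0.58/0.59 | 75/54/35/25% | 10/9/9/9% | 67/46/27/19% | 12.0 to 15.8 |

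Discrimination is weak throughout. The wrong-call share varies mainly with the proportion absent and the cut-off.

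**2. What a three-group Kruskal-Wallis result can hide.** Normal data were simulated with 40% absent and two present groups of 30% each, shifted by equal amounts below and above the absent group. The true absent-versus-present AUC is then 0.50. Share of 10,000 runs significant at 5%:

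| n | Shift 0.1 SD | 0.2 SD | 0.3 SD | 0.4 SD |
|---|---|---|---|---|
| 60 | 7.3% | 15.8% | 30.6% | 51.3% |
| 100 | 8.8% | 24.3% | 49.6% | 75.6% |
| 200 | 14.4% | 45.9% | 81.8% | 97.5% |

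**3. What a cut-off chosen on the same data does.** With the Youden cut-off selected and evaluated on the same boys (2,500 runs per case, same ranges as in step 1), the apparent Youden index exceeded the true one: from 0.18 against 0.10 up to 0.40 against 0.23. Exact 95% intervals covered 90-95%.

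Bootstrap intervals were also simulated (300 runs × 300 resamples; 40% absent at n = 60-200 with AUC 0.62 or 0.80, plus 20% and 70% absent at n = 100 with AUC 0.80). With the cut-off chosen in one resample and applied to a second, coverage was 93-100% for sensitivity, specificity, PPV and NPV. With choice and evaluation in the same resample, shifted by optimism, coverage for specificity fell to 30-63% under a fixed-specificity rule, because that rule pins specificity in the resample where the cut-off is chosen.

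**The case against.** The strongest points on the other side are these.

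- *The Mann-Whitney statistic divided by n1 × n0 is the AUC.* True, but the plan does not commit to reporting it. An AUC alone gives no cut-off or error rate, and a three-group Kruskal-Wallis test does not yield the absent-versus-present AUC.
- *The first illustration is a boundary case driven by assumed prevalence.* This stands as a limit on its use. Calling every boy absent would be wrong in 30-80% at the assumed 20-70% absent, so much of the spread is prevalence. The low AUC and low sensitivity do not depend on that.
- *The second illustration concerns only one of the two named tests and a symmetric pattern chosen for it.* Also fair. In the same scenario, Mann-Whitney on absent against pooled present was significant in only about 3-5% of runs. The risk exists because the plan does not say which test applies or how findings are pooled.
- *The variable can be inferred.* Abstract and Background point to volume and the three diameters, so the heavier gap is the unstated grouping.
- *The documents speak of status and never set absent versus present as the target.* Correct. That target follows from the laparoscopy decision, but the investigators should adopt it explicitly.
- *The bootstrap goes beyond the defect.* In part. A simpler interval would close the basic gap, since exact intervals at a same-data Youden cut-off still covered 90-95%. The optimism in the point estimates does need correcting.

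None of this supplies an accuracy measure that the plan commits to.

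**Conclusion.** The concern holds and should be fixed before analysis. The plan's own aim needs an estimate of how well size separates absent from present testes, and the Statistical Analysis section commits to none. This follows from reading the aim against the analysis and needs no assumed figure.

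The size is illustrative. Under the equal-variance binormal model, with n = 60-200 and 20-70% absent, a result exactly at p = 0.05 means an AUC of 0.58-0.68. The share of absent calls that are wrong is then 21-75% at the Youden point and 13-67% at 95% specificity, with sensitivity of 9-17% at the latter. A smaller p-value at the same n would mean better discrimination, but the plan would still not report it.

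**What to change.** Make a diagnostic-accuracy analysis primary and state the following before analysis:

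1. **Target and reference.** Laparoscopic finding as reference standard, absent versus present as the binary target. State how a testis passing through the DIR is classified. Add a sensitivity analysis under the other classification and, from the documented procedure, one that separates atrophied testes excised at inguinal exploration.
2. **Measures.** ROC curve and AUC with 95% CI for volume (primary) and each diameter (secondary).
3. **Cut-off rule.** For example, the cut-off that reaches a specificity for absent fixed in advance by the investigators. At that cut-off, report optimism-corrected sensitivity, specificity, PPV and NPV.
4. **Intervals.** Bootstrap 95% CIs that repeat the cut-off selection in each resample and apply the selected cut-off to a second, independent resample. Use exact binomial intervals only for a numerical cut-off fixed in advance.
5. **Conclusion.** The investigators state the accuracy they would need, and the conclusion rests on estimates and intervals. Keep the rank tests as descriptive, with variable and groups named.

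The cost is wording and some extra analysis. No new measurement is needed; the resampling may need a script beyond the named SPSS package. The downside is that the result may be less favourable or inconclusive. At 95% specificity in the first illustration, only about 4-16 boys would be called absent. Even with no wrong call at a cut-off fixed in advance, the exact two-sided 95% lower bound for PPV, 0.025^(1/m) with m boys called absent, is 48% for m = 5, 69% for m = 10 and 83% for m = 20.
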